This study uses a cross-over design to test a diet change plus a 10-12 hour eating window (Treatment A) compared to a diet change, an 8-hour eating window and one 36-60 hour fast per week (Treatment B) in subjects screened to have a minimum of five long COVID-19 symptoms. Fasting is for food only, but water is available. There is a two-week run-in with symptom surveys at the start (Week 0) and end (Week 2), followed by randomization to either ARM AB or ARM BA (with weekly symptom surveys). Since the water fasts are at the beginning of the week (with symptoms surveyed at the end of the week) there is a 5 day washout and then a cross-over to the other treatment for 4 weeks.

Study Hypothesis

Time-restricted eating and a no added sugars diet decreases Long Covid symptoms and symptoms scores. The addition of weekly water fasts and 8 hr time-restricted eating will result in a greater decrease of Long Covid symptoms than 10-12 hr restricted eating and a no added sugar diet alone over a four-week period.

Study Aims

This study aims to:

- a) Determine if the self-treatment of 36- or 60-hour water fasting once a week for a month reduces overall long COVID severity. If so, to what degree and what is the statistical significance of the results?
- b) Determine if eating in a 10-to-12-hour window daily and avoiding sugar for a month reduces overall long COVID severity. If so, to what degree and what is the statistical significance of the results?
- c) Determine if the self-treatment of 36- or 60-hour water fasting once a week for a month reduces the severity of twenty-eight common long COVID symptoms. If so, to what degree and what is the statistical significance of the results?
- d) Determine if eating in a 10 to 12 hour window daily and avoiding sugar for a month reduces the severity of twenty-eight common COVID symptoms. If so, to what degree and what is the statistical significance of the results?
- e) Determine which is more efficacious: "time-restricted eating, no sugar diet, and a weekly short water fast" OR "time-restricted eating, no sugar diet".

Study Significance and Background:

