1.1 Study Aims

1.1.5 **Primary aim:** Determine if self-treatment with 23- to 60-hour water fasting once per week in addition to eating in a daily 8-hour TRE window (i.e., daily 16-hour water fasting) and eating a low-sugar diet reduces overall Long COVID severity, as measured by sixty symptoms of Long COVID.

1.2.5 Secondary aims:

- 1.2.1.5 Determine if eating in a 10- to 12-hour TRE window daily (i.e., 12- to 14-hour daily fasting) and eating a low-sugar diet reduces overall Long COVID severity.
- 1.2.2.5 Determine if the self-treatment of 23- or 60-hour water fasting once per week for four weeks (in addition to 8-hour TRE and a low-sugar diet) reduces the severity of twenty-eight common Long COVID symptoms.
- 1.2.3.5 Determine if eating in a 10- to 12-hour window daily and avoiding sugar for four weeks reduces the severity of twenty-eight common COVID symptoms.
- 1.2.4.5 Determine which is more efficacious for reducing severity of Long COVID: a once-weekly 23- to 60-hour water fast with daily substantial 8-hour TRE (16-hour fasting) and a low-sugar diet OR a daily modestly-restricted TRE and low-sugar diet.

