2.1 Study Hypotheses

2.1.5 **Primary hypothesis**: The overall Long COVID symptom severity score is lower after 4 weeks of once-per-week 23- to 60-hour water-only fasting [in addition to eating in an 8-

hour daily TRE window (16-hour water fasting) and following a low sugar diet] than after 4 weeks of 10- to 12-hour daily TRE (12- to 14-hour water fasting) and a low-sugar diet.

2.2.5 Secondary hypotheses:

- 2.2.1.5 The overall Long COVID symptom severity score is lower after 1, 2, or 3 weeks of once-per-week water-only fasting (in addition to eating in an 8-hour window daily and a low sugar diet) than after 1, 2, or 3 weeks of 10- to 12-hour daily time-restricted eating and a low-sugar diet.
- 2.2.2.5 The overall Long COVID symptom severity score is lower after the initial 2-week run-in phase of 10- to 12-hour daily TRE and a low-sugar diet reduces Long COVID symptom severity scores.
- 2.2.3.5 The count of Long COVID symptoms is lower after 1, 2, 3, or 4 weeks of onceper-week water-only fasting (in addition to eating in an 8-hour window daily and a low sugar diet) than after 1, 2, 3, or 4 weeks of 10- to 12-hour daily timerestricted eating and a low-sugar diet.

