3.1 Analysis Plan

- 3.1.5 The study population will be evaluated using an intent-to-treat approach to the statistical analysis. All subjects who have data regarding symptom severity scores available at each time point will be included in the analyses.
- 3.2.5 Demographics, anthropometric variables, risk factors, COVID-19 vaccinations, other medications, and socioeconomic variables will be described as percentages or means with standard deviations.
- 3.3.5 Symptom severity scores will be compared between the two study arms using the two-sided paired T-test at each time point, as appropriate. Based on the randomized design of the study, it is expected that most if not all of these data elements will be balanced between the TRE arm and the Fasting arm of the study. Similar comparisons will also be performed to compare between the treatment arms for changes at weeks 1, 2, or 3 of each treatment to examine potential timing of the impact of those interventions.
- 3.4.5 The presence of individual symptoms at baseline, end of the run-in period, end of Fasting, end of TRE, and end of the 10-week trial will be summarized with percentages or means. Examination of overall changes in all participants for LC-score and numLCsym will use two-sided Student's T-test to evaluate the differences in means at baseline and the end of the 2-week run-in phase, and at baseline compared to the final week of the trial. A repeated measures general linear model will be used to test differences between the two trial arms across baseline and the 10 end-of-week measurements of the LC-score and numLCsym.
- 3.5.5 Adherence to the Fasting intervention will be tracked for each participant using self-reported assessment of whether the components of the intervention were followed each week of the study and will be reported as percentages.
- 3.6.5 Adverse events and major adverse events will be recorded for each participant and reported as percentages along with counts of events at each time point.
- 3.7.5 Analyses will use R Studio.
- 3.8.5 Exploratory analyses will examine other features of the data set
- 3.9.5 Subgroup analyses may be conducted using non-paired two-sided t-tests to identify statistically significant correlations between mean percent decreases in the primary measures and various baseline characteristics.

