5.0 Limitations

1.1 Trial limitations include the lack of a parallel standard control arm, lack of randomization to just one treatment for each trial participant (due to the crossover design), a limited sample size, evolving definitions of Long COVID in the field, and a short duration of treatment by each intervention during the study.

2.1 Participant limitations include an open-label set of interventions conducted without blinding of participants to the treatment that they receive, self-selection for participation, and self-reporting of symptoms.

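### The diet/TRE-alone aims ask for an efficacy answer, but no comparison in the trial isolates diet/TRE; the only matching test is an uncontrolled week 0 to week 2 change

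*Combined protocol and SAP*

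**What the plan says.** **Aims and hypotheses.** SAP 1.2.1.5 sets out to "Determine if eating in a 10- to 12-hour TRE window daily", together with a low-sugar diet, lowers overall severity. SAP 1.2.3.5 goes further: "Determine if eating in a 10- to 12-hour window daily and avoiding sugar for four weeks reduces the severity of twenty-eight common COVID symptoms". Hypothesis 2.2.2.5, on the run-in, ends with the statement that the regimen's "low-sugar diet reduces Long COVID symptom severity scores". The protocol's Study Hypothesis is flatly causal: "Time-restricted eating and a no added sugars diet decreases Long Covid symptoms and symptoms scores". Protocol aims b and d, on the same regimen, each add "If so, to what degree and what is the statistical significance of the results".

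**Design.** Protocol item 15 puts all participants on the no-added-sugars diet and a 10 to 12 hour window for the two baseline weeks. Each sequence then has four weeks of Treatment A (diet, 10-12 h window) and four of Treatment B (diet, 8 h window, weekly fast).

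**Tests.** SAP 3.4.5 applies a two-sided t-test to LC-score and numLCsym in all participants, to "evaluate the differences in means at baseline and the end of the 2-week run-in phase", and again "at baseline compared to the final week of the trial". The presence of individual symptoms is only summarised. The comparisons between treatments in 3.3.5 set fasting against TRE.

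**Caveat.** SAP 5.0 opens with "Trial limitations include the lack of a parallel standard control arm" and goes on to list open-label treatment, self-selection and self-reported symptoms.

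**The concern.** The aims ask whether diet/TRE lowers severity, and a p-value is to accompany the answer. A before-after t-test shows whether the mean moved, not why. With no group off the regimen, a fall between week 0 and week 2 has several explanations besides diet: spontaneous change, expectation in unblinded people who chose to join a diet study, drift in self-report, and whatever else changed at entry. Followed literally, the plan lets a significant week 2 result be reported as evidence that diet/TRE works. For a condition that both documents describe as having no proven treatment, that claim would travel.

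**Working it through.** **1. Which comparison could answer the aim?**

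| Comparison | What differs | Isolates diet/TRE? |
|---|---|---|
| Week 0 vs week 2, all participants (3.4.5) | Time, diet/TRE and anything else changed at entry | No, but it is the only test confined to diet/TRE |
| Week 0 vs final week, all participants (3.4.5) | As above, plus four weeks of fasting in everyone; half end on fasting, half on TRE | No; it estimates neither treatment |
| Fasting vs TRE (3.3.5, and the repeated-measures model) | Weekly fast and narrower window; diet on both sides | No; it estimates what fasting adds |
| 28 symptoms over four weeks of TRE (aim 1.2.3.5) | No before-after test is named | Not tested |

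**2. The plan's own sample-size figure.** SAP 4.0, 2.1.5 gives 40 to 90 per arm without effect size, SD, alpha or power. It cannot be reproduced and does not concern these aims.

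**3. How small a fall is significant?** Inputs: n = 58 (SAP 2.0); two-sided test (3.4.5); alpha 0.05 (assumed); paired form (assumed, since 3.4.5 does not say). The threshold in units of the SD of change is t(0.975, 57)/√58 = 2.002/7.616 = **0.26**.

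**4. Chance of a significant improvement when diet has no effect.** Let d be the non-diet fall in cross-sectional SD and r the test-retest correlation; both are assumptions. The standardised change is d/√(2(1−r)). At r = 0.7 the divisor is √0.6 = 0.775. The noncentrality is that value times √58, and the probability is the upper tail of the noncentral t on 57 df beyond 2.002.

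| d | Standardised change | Noncentrality | Probability |
|---|---|---|---|
| 0 | 0 | 0 | 2.5% |
| 0.1 | 0.129 | 0.98 | 16% |
| 0.2 | 0.258 | 1.97 | 49% |
| 0.3 | 0.387 | 2.95 | 83% |

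For d = 0.2, moving r from 0.6 to 0.8 gives 39% to 66%.

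**5. If the test were run unpaired.** The threshold becomes 1.981 × √(2/58) = 0.368 cross-sectional SD. At r = 0.7 the true standard error is √(0.6/58) = 0.102, so falls of 0.1, 0.2 and 0.3 SD lie 2.63, 1.65 and 0.67 standard errors below it. By the normal tail these give about 0.4%, 5% and 25%. The size of the risk depends on an unstated choice; the lack of attribution does not.

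**6. Regression to the mean from the entry rule.** The threshold of five symptoms is applied at the screening survey, not to the week 0 score. The expected fall is (r₀ − r₂) × λ, where r₀ and r₂ are the correlations of the screening score with weeks 0 and 2, and λ is the mean of a normal variable truncated at the pass mark (0.798, 0.350 or 0.109 if 50%, 80% or 95% of applicants pass). With r₀ = r₂ it is zero. With 0.8 falling to 0.7 it is 0.08, 0.035 or 0.01 SD.

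**The case against.** The strongest reply is that the SAP already concedes the missing control, the open label and the self-report; that the primary hypothesis is the randomised contrast, which this leaves untouched; and that a labelled before-after change is legitimate description even with a p-value. The first two statements are true. But section 5.0 is general and does not limit what may be concluded under 1.2.1.5, 1.2.3.5 or 2.2.2.5, whose wording goes beyond description.

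Four stronger readings are tempting and are not supported.

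- *The plan will very probably declare diet/TRE effective even if it is inert.* The probability runs from 16% to 83% over the assumed drifts and is lower if the test is unpaired. Nothing in the documents fixes the drift.
- *Selecting people for symptoms guarantees a fall by regression to the mean.* Step 6 shows that this may be nil or small. Protocol item 16 also has women with predictable monthly flares take the first survey away from the flare, which avoids some inflated baselines.
- *Stopping drugs and supplements biases the result towards benefit.* The documents require willingness to stop supplements and, for users of listed drugs, that these can be halted (or, for cholesterol drugs, reduced). They do not say how many are affected or when stopping occurs relative to week 0, and the effect on symptoms could go either way.
- *Both t-tests are designated as tests of diet/TRE.* SAP 3.4.5 presents them as overall changes in all participants and ties the final-week test to no diet/TRE aim.

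**Conclusion.** The concern holds as a mismatch between what these aims ask and what the design can show. That conclusion rests on the documents alone: diet/TRE is given to everyone from week 0 and the diet continues in both treatments, so no analysis of these data can attribute a change to it. For 1.2.1.5 and 2.2.2.5 the available test is uncontrolled; for 1.2.3.5 no before-after test is named at all. The size is conditional: a fall of 0.26 SD of change from any cause reaches significance, and 16%, 49% or 83% applies to non-diet falls of 0.1, 0.2 or 0.3 SD, given n = 58, alpha 0.05, a paired test and r = 0.7. The main reasons for caution are natural course and unblinded self-report, not the entry threshold. The change should be made, since it alters what may be concluded at little cost.

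**What to change.** - Reword SAP 1.2.1.5, 1.2.3.5 and 2.2.2.5, and protocol aims b and d, as describing the change during diet/TRE. Treat the protocol's Study Hypothesis sentence the same way.
- Report the week 0 to week 2 change in all participants as a mean with 95% CI, based on within-person differences.
- Report separately the week 2 to week 6 change in Arm AB, with 95% CI. This is the only four-week TRE period not preceded by fasting, so it best matches the four weeks in 1.2.3.5. It remains uncontrolled and, with 29 people, imprecise.
- Label baseline to final week as overall change across the whole programme, attributable to neither treatment. Splitting the week 2 to final-week change by sequence would not help, because each sequence has by then had four weeks of each treatment.
- State in the SAP that no effect of diet/TRE alone can be concluded.

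**Cost.** Some wording and one small table, with no new data. The secondary efficacy claim for diet/TRE is given up. Keeping it would need a randomised usual-diet group: by n = 2(1.960 + 0.842)²/d² = 15.7/d², 175, 99 or 63 per arm for standardised differences of 0.3, 0.4 or 0.5 at 80% power (alpha 0.05, assumed). The trial has 29 per sequence.

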2.1 Study Hypotheses

2.1.5 **Primary hypothesis**: The overall Long COVID symptom severity score is lower after 4 weeks of once-per-week 23- to 60-hour water-only fasting [in addition to eating in an 8-

hour daily TRE window (16-hour water fasting) and following a low sugar diet] than after 4 weeks of 10- to 12-hour daily TRE (12- to 14-hour water fasting) and a low-sugar diet.

2.2.5 Secondary hypotheses:

- 2.2.1.5 The overall Long COVID symptom severity score is lower after 1, 2, or 3 weeks of once-per-week water-only fasting (in addition to eating in an 8-hour window daily and a low sugar diet) than after 1, 2, or 3 weeks of 10- to 12-hour daily time-restricted eating and a low-sugar diet.
- 2.2.2.5 The overall Long COVID symptom severity score is lower after the initial 2-week run-in phase of 10- to 12-hour daily TRE and a low-sugar diet reduces Long COVID symptom severity scores.
- 2.2.3.5 The count of Long COVID symptoms is lower after 1, 2, 3, or 4 weeks of onceper-week water-only fasting (in addition to eating in an 8-hour window daily and a low sugar diet) than after 1, 2, 3, or 4 weeks of 10- to 12-hour daily timerestricted eating and a low-sugar diet.

2.0 Study Population

The trial population consists of 58 individuals, including 29 randomized to 4 weeks of once-per-week 23-60 hour water-only fasting plus daily 8-hour TRE (16-hour daily water fasting) and a low-sugar diet followed by 4 weeks of 10- to 12-hour daily TRE (daily 12- to 14-hour water-only fasting) and a low-sugar diet, and the other 29 randomized to 4 weeks of daily 10-12 hour TRE (daily 12- to 14-hour water-only fasting) and a low-sugar diet followed by 4 weeks of once-per-week 23-60 hour fasting plus daily 8-hour TRE (16-hour daily water fasting) and a low-sugar diet. All participants engaged in 10 weeks of the study protocol, including a 2-week run-in period of daily 10- to 12-hour TRE (daily 12- to 14-hour water-only fasting) and a low-sugar diet.

- 1.1 Inclusion Criteria: participants must be adults, 18 to 69 years of age; they must have 5 or more of the 28 common Long COVID symptoms, they must reside in the United States of America, and they must be willing to stop the consumption of any nutritional supplements that may activate autophagy.
- 2.1 Exclusion Criteria: At baseline, participants could not have a body mass index below 20 kg/m², could not be pregnant or breastfeeding, and could not have had a SARS-CoV-2 infection within 45 days. Further, they could not carry a diagnosis of type 1 or type 2 diabetes and could not have a history of any eating disorder.
- 3.1 Data Acquisition: All participant data were collected through pragmatic electronic means in REDCap. Weekly symptom and adherence data were collected through similar REDCap forms. All data were stored in REDCap until the end of the study enrollment and follow-up period was complete for all trial participants.

3.0 Outcomes, Exposures, and Other Variables

1.1 Trial Intervention and Control Arms

- 1.1.5 Active "Control" Arm: a low-sugar diet with a 10- to 12-hour daily TRE eating window and water-only fasting for the other daily 12 to 14 consecutive hours.
- 1.2.5 Intervention Arm: a low-sugar diet with a more restrictive 8-hour daily TRE eating window and 16 consecutive hours of daily fasting, along with a once-weekly 23- to 60-hour water-only fast.

2.1 Trial Endpoints

2.1.5 **Primary endpoint**: The primary trial endpoints are: 1) a composite of symptom severity scores for 28 common Long COVID symptoms and 32 less common symptoms, and 2) a sum of the presence or absence of the 60 symptoms.

2.2.5 Secondary endpoints

- 2.2.1.5 A composite of symptom severity scores for 28 common Long COVID symptoms.
- 2.2.2.5 Each of the 28 common Long COVID symptom severity scores individually.
- 2.2.3.5 The count of the 28 common Long COVID symptoms that are present.
- 2.2.4.5 The count of the 32 less common Long COVID symptoms that are present.
- 2.2.5.5 Adherence to the assigned trial intervention.

2.3.5 Other study data elements: percent resolution of each Long COVID symptom.

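### The 28 individual symptom scores are secondary endpoints with significance asked for but no multiplicity control or exploratory label, so the chance of falsely naming a symptom as improved by fasting is well above that of a single test

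*Combined protocol and SAP*

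**What the plan says.** **Endpoints.** SAP section 3.0, secondary endpoint 2.2.2.5, reads "Each of the 28 common Long COVID symptom severity scores individually". The composite of the same 28 scores is a separate item, 2.2.1.5, so the individual scores are endpoints in their own right.

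**Aims.** Protocol aim (c) asks whether weekly water fasting "reduces the severity of twenty-eight common long COVID symptoms. If so, to what degree and what is the statistical significance of the results"; aim (d) asks the same of the diet-only treatment. SAP secondary aim 1.2.2.5 carries aim (c) forward: whether the fasting regimen "reduces the severity of twenty-eight common Long COVID symptoms". SAP 1.2.3.5 does the same for aim (d). The SAP versions leave out the request for significance.

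**Test.** SAP 3.3.5: "Symptom severity scores will be compared between the two study arms using the two-sided paired T-test at each time point, as appropriate". It adds that similar analyses will "compare between the treatment arms for changes at weeks 1, 2, or 3 of each treatment".

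**What is descriptive.** SAP 3.4.5 says that the presence of individual symptoms, at time points running to the end of the "10-week trial will be summarized with percentages or means". That covers presence, not severity. SAP 3.8.5 allows exploratory analyses of other features of the data and does not mention the 28 scores.

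**What is absent.** Neither document states a significance level, a multiplicity adjustment, a testing order or false discovery control, and nothing marks the 28 scores as exploratory.

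**The concern.** Twenty-eight scores are listed one by one, significance is asked for, and the only test given for severity scores is an unadjusted t-test. An analyst following the plan would most naturally run that test 28 times and report the symptoms with small p-values. Some of those could be chance findings.

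The stake is the list of symptoms said to respond to fasting. The protocol presents the regimen as simple, inexpensive and something most people could try if it works. The SAP's limitations section acknowledges that participants are unblinded and report their own symptoms. A named symptom benefit from this trial could therefore be acted on directly.

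This is separate from how the primary endpoints are tested, and it does not touch the primary hypothesis, which concerns the overall severity score after four weeks.

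**Working it through.** The documents give no error rate for the symptom family, so there is no plan figure to reproduce.

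**Inputs**
- Number of tests: 28 (secondary endpoint 2.2.2.5), one fasting-versus-TRE contrast each, at one time point.
- Test: two-sided paired t (SAP 3.3.5).
- N = 58 (SAP section 2.0: "The trial population consists of 58 individuals"). N sets only the degrees of freedom here. With no true effect, each test keeps its nominal error rate at any N.
- Alpha: not stated. Assumed 0.05 two-sided, which is 0.025 in the tail favouring fasting.
- Correlation between symptom differences: not stated. Assumed equal for all pairs, from 0 to 0.7.
- No true effect on any of the 28 symptoms.

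**Expected false positives, whatever the correlation**
- Either direction: 28 × 0.05 = 1.4.
- Favouring fasting: 28 × 0.025 = 0.7.

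**At least one false positive, independent symptoms**
- Either direction: 1 − 0.95^28 = 76.2%.
- Favouring fasting: 1 − 0.975^28 = 50.8%.

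**Correlated symptoms**
Each participant's difference for a symptom was simulated as √ρ × (shared normal term) + √(1−ρ) × (own normal term), followed by 28 paired t-tests on 58 participants. The table shows 100,000 repetitions. The last column applies the Benjamini-Hochberg rule at 5% to the same data.

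| ρ | Any, either direction | Any, favouring fasting | Any, after Benjamini-Hochberg |
|---|---|---|---|
| 0 | 76.1% | 50.9% | 5.0% |
| 0.3 | 64.4% | 34.1% | 4.7% |
| 0.5 | 49.9% | 25.0% | 4.0% |
| 0.7 | 33.8% | 16.8% | 2.9% |

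Shorter simulations of the same set-up agree to within about two percentage points.

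**Sensitivity, independent symptoms**
- Alpha 0.01: either direction 1 − 0.99^28 = 24.5%; favouring fasting 1 − 0.995^28 = 13.1%.
- Alpha 0.10: either direction 1 − 0.90^28 = 94.8%; favouring fasting 1 − 0.95^28 = 76.2%.
- Only 14 of the 28 symptoms truly null, alpha 0.05: either direction 1 − 0.95^14 = 51.2%; favouring fasting 1 − 0.975^14 = 29.8%.

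**Cost in sensitivity**
Detectable standardised paired difference at N = 58 and 80% power, normal approximation:
- Unadjusted: (1.960 + 0.842)/√58 = 0.37 SD.
- Bonferroni, per-test alpha 0.05/28 = 0.00179: (3.124 + 0.842)/√58 = 0.52 SD.

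Benjamini-Hochberg lies between the two, because its threshold for the k-th smallest p-value is k × 0.05/28.

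**The case against.** The strongest reply is that the SAP never says each symptom will be tested. SAP 3.3.5 speaks of severity scores in general, and as appropriate. The hypotheses in SAP section 2.1 cover only the overall score and the symptom count. The one analysis sentence that mentions individual symptoms, in 3.4.5, is descriptive. The aims could be answered by the 28-symptom composite. Much of this stands: one-by-one testing is a joint reading of the aims, the endpoint list and 3.3.5. It remains the natural reading, because the individual scores are listed apart from the composite and no other analysis is given for them.

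Three stronger readings are tempting, and the documents do not support them.

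- **A reader might infer that a false claim of benefit from fasting is likely.** The 76% figure counts both directions, including symptoms that look worse on fasting. The fasting tail alone only just exceeds one half, and only if all 28 symptoms are independent and null. Symptoms reported by the same person are plausibly correlated, and at 0.3 the figure is already near one third.
- **A reader might count 56 tests, 28 for each treatment.** SAP 3.3.5 gives one contrast between treatments per score, and the before-after tests in 3.4.5 are for the LC-score and numLCsym only. No within-treatment test per symptom is specified.
- **A reader might add weeks 1 to 3 for every symptom, which would raise the risk.** The hypotheses for those weeks concern the overall score and the symptom count, so those tests are not counted here.

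It is also fair to say that these are secondary endpoints and that an all-null family is the worst case.

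**Conclusion.** The concern holds in a limited form. If the 28 scores are tested as the passages jointly imply, the chance of at least one false improvement credited to fasting is roughly 16% to 51% at one time point, or about 6 to 20 times the 2.5% for a single test. In either direction the range is about 32% to 76%. These ranges rest on an assumed alpha of 0.05, assumed equal correlations from 0.7 down to 0, and no true effect on any symptom. If some symptoms truly respond, the risk is lower but still well above that of one test. This is an inexpensive improvement to a secondary analysis.

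**What to change.** Add to SAP 3.3.5:
- State the two-sided significance level.
- Treat the 28 fasting-versus-TRE contrasts at the end of week 4 of each treatment as one family.
- Report each estimate with its 95% CI and a Benjamini-Hochberg adjusted p-value (5% false discovery rate).
- Name a symptom as improved only on the adjusted value.
- Keep per-symptom results at other weeks, and per-symptom before-after changes, descriptive.

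An acceptable alternative is to label all per-symptom results exploratory and report estimates and CIs with no significance claims.

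The adjustment takes a sentence or two in the SAP and one line of R, with no new data or participants. Its downside is that fewer individual symptoms will reach significance. Benjamini-Hochberg also limits the expected share of false names on the list; it does not guarantee that the list has none when some symptoms truly respond.
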